13.5 Accrual

The projected accrual to this trial is approximately 6 non-small cell lung cancer patients and 3 colorectal cancer patients per month. We estimate that 24 months will be required to complete study accrual.

PLANNED ENROLLMENT REPORT

Racial Categories	Ethnic Categories				Total
	Not Hispanic or Latino		Hispanic or Latino		
	Female	Male	Female	Male	
American Indian/ Alaska Native	5	5	0	0	10
Asian	5	5	0	0	10
Native Hawaiian or Other Pacific Islander	0	0	0	0	0
Black or African American	15	15	5	5	40

Racial Categories	Ethnic Categories				Total
	Not Hispanic or Latino		Hispanic or Latino		
	Female	Male	Female	Male	
White	40	40	10	10	100
More Than One Race	5	5	5	5	20
Total	70	70	20	20	180

PHS 398 / PHS 2590 (Rev. 08/12 Approved Through 8/31/2015)

OMB No. 0925-0001/0002

13.6 Interim Safety Analysis

NSCLC: For an early and detailed safety assessment, complete review of the adverse event data for the first 10 patients assigned to MEDI4736(durvalumab)/tremelimumab/high-dose RT and for the first 10 patients assigned to treatment with MEDI4736(durvalumab)/tremelimumab/low-dose RT will occur after completion of one cycle (4 weeks) of therapy. If three or more patients within a therapy arm experience one or more dose-limiting toxicities, the addition of RT will be considered too toxic and enrollment to that arm will stop.

Colorectal Cancer: Concurrent with the end of the first stage of each Simon design, a complete safety review of adverse event data will be conducted for each treatment after completion of two cycles of therapy. If three or more patients within a therapy experience one or more severe or pre-specified dose-limiting toxicities, enrollment to that arm will stop.

The table below summarizes the probability of observing three or more severe or unexpected toxicities in the first 10 patients of a cohort for various underlying true probabilities. If the true incidence of severe or unexpected toxicities is 25% or higher, then the probability is at least 0.47 that three or more patients will be observed with these toxicities at the time of the early safety monitoring.

True Incidence of Unexpected or Severe Toxicity	Probability of Observing Three or More Patients with Toxicity among First 10
10%	0.07
15%	0.18
20%	0.33
25%	0.47
30%	0.62

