4.4 General Guidelines

Following registration, patients should begin protocol treatment within 28 days. Issues that would cause treatment delays should be discussed with the Principal Investigator. If a patient does not receive protocol therapy following registration, the patient's registration on the study may be canceled. The Study Coordinator should be notified of cancellations as soon as possible.

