- 3) Prescriptions: Patients randomized to higher dose radiation arm (Arm A) will be prescribed a total dose of 24 Gy in 3 fractions. Patients randomized to the lower dose radiation (Arm B) will be prescribed a total dose of 2 Gy in 4 fractions to be repeated with each of the first 4 cycles (total overall dose 8 Gy). In cohort 1 (NSCLC), patients randomized to the no radiation arm (Arm C) will not receive any radiation. Please also

refer to schema below:

NSCLC Cohort- Cohort 1

Colorectal Cohort- Cohort 2

*0.5 Gy BID x2 days repeated q4weeks with durvalumab / tremelimumab

Only photons treatments are allowed, and volumetric treatment planning is mandated. Planning may be 3D conformal, IMRT or SBRT, as appropriate to each individual case / lesion to achieve coverage of the PTV target and maintain normal tissue tolerance. The percentage PTV covered to 100% of the prescription dose will be reported along with the maximum hotspot; reasonable effort should be made to keep this greater than 95% while maintaining normal tissue dose constraints as indicated below. Bolus may be used as appropriate. Note that for patients prescribed 24 Gy in 3 fractions, maximum hotspot should not exceed 115% in any case.

- 4) Timing of radiation treatment:
- Arm A: Higher dose radiation. Radiation will start on week 2. Three treatments of 8 Gy will generally be delivered every other day. They must not be delivered on consecutive calendar days and more than one fraction may not be delivered on the same day. The total treatment time must not extend over more than 10 calendar days. Shorter treatment courses (approximately 5 days) are favored, but no specific

treatment schedule is mandated to account for weekends, holidays, machine maintenance, etc.

- Arm B: Lower dose radiation: Radiation will start on week 2. Four treatments of 0.5 Gy will be delivered no more frequently than every 6 hours and will be scheduled to occur twice per day over a period of two days. Although treatment is allowed to extend over three calendar days in the case of machine maintenance or patient illness, this is strongly discouraged.

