5.2 Definition of Dose-Limiting Toxicity

Although there is significant safety data for the MEDI4736/ tremelimumab treatment and palliative radiation, the combination is relatively untested, although emerging safety data suggests the combination of the two treatments (specifically in regards to limited palliative radiation treatment fields) do not increase the rates of irAE or radiation toxicity [64]. Although this retrospective data compares favorably to previous studies testing combined checkpoint inhibition, to provide greater confidence in the safety of radiation and combined checkpoint inhibition, DLT's will be monitored in a step-wise fashion and over time. As part of the safety assessment for the NSCLC cohort, complete review of the adverse event data for the first 10 patients assigned to MEDI4736(durvalumab)/tremelimumab/high-dose RT and for the first 10 patients assigned to treatment with MEDI4736(durvalumab)/tremelimumab/low-dose RT will occur after completion of two cycles of therapy. If three or more patients within a therapy arm experience one or more pre-specified dose-limiting toxicities the addition of RT will be considered too toxic and enrollment to that arm will stop. If this occurs in the high-dose radiation arm, all safety data from that arm will be reviewed and a protocol amendment may be considered.

Concurrent with the end of the first stage of each Simon design for the colorectal cohort, a complete safety review of adverse event data will be conducted for each treatment. If three of more patients within a therapy experience one or more pre-specified dose-limiting toxicities, enrollment to that arm will stop.

Dose-limiting toxicity (DLT) is based on the CTEP Active Version of the NCI Common Terminology Criteria for Adverse Events (CTCAE). Although we will continue to monitor toxicity over time, the DLT period in this study refers to toxicities experienced during the first 4 weeks of treatment.

DLTs will be graded according to the National Cancer Institute's CTCAE v5.0 https://ctep.cancer.gov/protocolDevelopment/electronic_applications/ctc.htm (<http://ctep.cancer.gov/forms/CTCAEv45.pdf>).

A DLT will be defined as any <<Grade 3 or higher>> toxicity that occurs during the DLT evaluation period. Toxicity that is clearly and directly related to the primary disease or to another etiology is excluded from this definition. The following will be DLTs:

- Any Grade 4 irAE
- Any \geq Grade 3 colitis

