While rules for adjudicating DLTs are specified above, an AE that is Grade $<$ 3 or listed as exempt above may also be defined as a DLT after consultation with the sponsor and Investigators, based on the emerging safety profiles of MEDI4736 and tremelimumab. Likewise, subjects who become not evaluable for DLT because they discontinued or interrupted treatment due to toxicities other than DLTs will be counted as DLT subjects using the same criteria as other DLTs (Grade 3 or higher toxicity that occurs during the DLT evaluation period and excluding toxicity that is clearly and directly related to the primary disease or to another etiology.)

Management and dose modifications associated with the above adverse events are outlined in Section 6.

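### In the NSCLC cohort the 3-of-10 toxicity stop counts patients assigned to an RT arm rather than DLT-evaluable patients, so the Section 13.6 table is an upper limit on its sensitivity to toxicity in irradiated, fully observed patients

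*Combined protocol and SAP*

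**What the plan says.** - **Who is counted.** Section 13.6 takes, for NSCLC, "the first 10 patients assigned to MEDI4736(durvalumab)/tremelimumab/high-dose RT" and the first 10 in the low-dose arm. Section 5.2 uses the same basis.
- **Rule.** "If three or more patients within a therapy arm experience one or more dose-limiting toxicities, the addition of RT will be considered too toxic". The arm then closes to accrual.
- **Window.** Section 5.2: "the DLT period in this study refers to toxicities experienced during the first 4 weeks of treatment".
- **Timing of the NSCLC review.** Section 13.6 says it "will occur after completion of one cycle (4 weeks) of therapy"; Section 5.2 says it "will occur after completion of two cycles of therapy".
- **Radiation.** Section 5.1 says for both RT arms: "Radiation will start on week 2". Section 6 (Additional Information) defers remaining radiation when drug is held, until a week after the next cycle starts. An exception applies where the field is clearly unrelated to the event and the patient is stable.
- **Before treatment.** Section 4.4: "Following registration, patients should begin protocol treatment within 28 days". It allows the registration of a never-treated patient to be cancelled.
- **Evaluability.** Sections 11.1.1 and 13.9.1 make patients evaluable for toxicity once first treated; 13.9.1 adds that this applies whether or not RT is given. Section 5.2 addresses "subjects who become not evaluable for DLT because they discontinued or interrupted treatment due to toxicities other than DLTs" and counts them as DLT subjects, under the same Grade 3-or-higher criteria.

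**The concern.** The rule's verdict is about adding radiation, but membership of the 10 depends on assignment alone. A dosed patient who leaves before week 2, or before week 4, for progression, withdrawal or intercurrent illness (all reasons to stop in Section 5.4) stays in the 10 as a patient without a DLT. So does a patient whose radiation is deferred past week 4 by a drug hold for a Grade 2 event. Section 5.2 uses the idea of a patient not evaluable for DLT, but never defines it and settles it only for those who stop because of toxicity.

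Each such patient makes the 3-of-10 threshold harder to reach for a given toxicity rate among those actually irradiated. Section 5.2 itself calls the combination relatively untested, so the review should have the sensitivity its table suggests.

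**Working it through.** **Inputs.** From Section 13.6: 10 patients per RT arm, threshold 3, and the table of stop probabilities. From Section 5.2: a 4-week window. From Section 5.1: a 28-day cycle, with RT from week 2. The number k of the 10 who are uninformative about RT toxicity is not in the documents; I assume 0 to 3. The DLT risk q of those k patients is not given either; I take 0, 10% and 15%.

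**Step 1: reproduce the table.** P(X ≥ 3) = 1 − Σ(x=0..2) C(10, x) pˣ(1 − p)^(10−x).

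| True incidence p | Printed | Exact |
|---|---|---|
| 10% | 0.07 | 0.0702 |
| 15% | 0.18 | 0.1798 |
| 20% | 0.33 | 0.3222 |
| 25% | 0.47 | 0.4744 |
| 30% | 0.62 | 0.6172 |

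For p = 25%: 1 − (0.0563 + 0.1877 + 0.2816) = 0.4744. The table is Binomial(10, p), so all 10 patients carry the full risk p. The 20% row should print 0.32.

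**Step 2: can a patient be in the 10 yet uninformative?** The next cycle begins in week 5 at the earliest, so radiation deferred by a drug hold restarts in week 6 at the earliest. The DLT window closes at week 4. The patient has been dosed, so is evaluable under 13.9.1, and was assigned, so is counted under 13.6. If the hold was for a Grade 2 event, the Grade 3 condition in Section 5.2 keeps it from being a DLT unless the event meets another listed criterion. Moving the review to two cycles does not change this, because the window stays at 4 weeks.

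**Step 3: the k patients contribute no DLT (q = 0).** The stop probability is P(X ≥ 3) for Binomial(10 − k, p).

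| k | p = 25% | p = 30% |
|---|---|---|
| 0 | 0.474 | 0.617 |
| 1 | 0.399 | 0.537 |
| 2 | 0.321 | 0.448 |
| 3 | 0.244 | 0.353 |

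**Step 4: the k patients keep a drug-only DLT risk q.** The stop probability is Σ(j=0..k) C(k, j) qʲ(1 − q)^(k−j) · P(X₁₀₋ₖ ≥ 3 − j). For k = 1, p = 25%, q = 10%: 0.9 × 0.399 + 0.1 × 0.700 = 0.429.

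| k | p = 25%, q = 10% | p = 30%, q = 10% | p = 25%, q = 15% |
|---|---|---|---|
| 1 | 0.429 | 0.564 | 0.444 |
| 2 | 0.383 | 0.507 | 0.414 |
| 3 | 0.337 | 0.446 | 0.383 |

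**Step 5: after the fix.** With 10 evaluable patients and p read as incidence per evaluable patient, the Step 1 values apply again: 0.474 at 25% and 0.617 at 30%.

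**The case against.** **The table may be right as it stands.** It does not say to whom its incidence refers. Read per assigned patient, Binomial(10, p) is exact however many miss radiation. A reader might infer that the stated value of at least 0.47 at 25% is false as soon as one patient is not evaluable; the documents do not support that, because it depends on this reading. What stands is that a per-assigned incidence suits poorly a rule whose verdict is on adding RT.

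**Never-treated patients are largely handled.** Sections 11.1.1 and 13.9.1 start toxicity evaluability at first treatment, Section 4.4 permits cancellation, and a review after completed therapy presupposes treated patients. A reader might infer from the 28-day interval that undosed patients fill the 10. The documents show only a wording conflict with assigned.

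**Toxicity leavers who meet the Section 5.2 criteria** count as DLTs and do not dilute the rule.

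**Early loss may be rare.** Radiation starts in week 2, Section 3.1.5 asks for ECOG 0–1, the first on-treatment scan is in week 7 or 8, and Section 5.8 allows treatment past first progression. These points limit k without fixing it. Section 11.1.1 itself foresees progression before the end of cycle 1, and the drug-hold route does not depend on progression.

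**Other safeguards exist.** A reader might infer that this is the only formal early safety gate. It is not: Sections 5.2 and 13.6 set a three-patient stop for each colorectal arm, 13.8.1 pauses a regimen when 33% or more have severe toxicities after the early review, and 12.1 requires ongoing review. These reduce what is at stake but do not define who belongs in the NSCLC 10.

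**Conclusion.** The point holds for the NSCLC cohort. Sections 13.6 and 5.2 use assigned patients, ask for neither RT exposure within the window nor completion of it, and replace nobody. The printed probabilities are therefore an upper limit on sensitivity to toxicity among irradiated, fully observed patients, provided that those who miss RT have no higher DLT risk than those who receive it. With no uninformative patients nothing is lost. With one to three, the stop probability at a true 25% falls from 0.47 to between 0.40 and 0.24 if they contribute no DLT, or to between 0.43 and 0.34 at an assumed 10% drug-only risk. Both k and q are assumptions; the documents give neither.

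The assigned wording should not be carried over to the colorectal cohort, whose review is tied to the 10 patients of Simon stage 1. The 0.33 entry is a minor slip that changes no decision. The two review timings for NSCLC contradict each other and must be reconciled.

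**What to change.** 1. In Sections 13.6 and 5.2, base the NSCLC review on the first 10 DLT-evaluable patients per RT arm: those who had a DLT at any point in the 4-week window, or who received RT within the window and completed it. Requiring one fraction at any time would not be enough, because deferred radiation can fall after week 4.
2. Keep the Section 5.2 provision for toxicity leavers. Replace other non-evaluable patients for this safety count only, and leave the threshold and the efficacy analysis unchanged.
3. Reconcile assigned (5.2, 13.6) with toxicity evaluability from first treatment (13.9.1), and the one-cycle review (13.6) with the two-cycle review (5.2).
4. State under the table that incidence is per DLT-evaluable patient, and print 0.32 in the 20% row.

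**Cost.** A sentence or two in each section, and a review that may wait for a few more patients. Section 13.5 projects about 6 NSCLC patients per month over three equal arms, so 6/3 = 2 per arm per month: each replacement takes about half a month to accrue, plus its own window. Others may be treated on the arm meanwhile. Section 4.3.2 already plans slot enrollment for the first 20 patients per NSCLC arm, which leaves room for replacements and a means of controlling that exposure.

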1. OBJECTIVES

1.1 Primary Objectives

NSCLC Cohort:

1. To assess safety and tolerability of combined checkpoint blockade with MEDI4736(durvalumab) and tremelimumab alone or with high or low-dose radiation in NSCLC
2. To compare the overall response (excluding the irradiated lesion(s)) between combined checkpoint blockade with MEDI4736 and tremelimumab alone or combined checkpoint blockade with low or high dose radiation.

Colorectal Cohort:

1. To assess safety and tolerability of combined checkpoint blockade with MEDI4736 and tremelimumab with high or low-dose radiation
2. To determine the overall response rate (excluding the irradiated lesion(s)) with combined checkpoint blockade with MEDI4736 and tremelimumab with either low or high dose radiation.

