A fixed dosing approach is preferred by the prescribing community due to ease of use and reduced dosing errors. Given expectation of similar PK exposure and variability, we considered it feasible to switch to fixed dosing regimens. Based on an average body weight of 75 kg, a fixed dose of 750 mg Q2W durvalumab is equivalent to 10 mg/kg Q2W, 1500 mg Q4W durvalumab is equivalent to 20 mg/kg Q4W, and 75 mg Q4W tremelimumab is equivalent to 1 mg/kg Q4W.

The safety of durvalumab + tremelimumab combination therapy was initially evaluated in the ongoing dose escalation and dose expansion Study 006, in patients with NSCLC, and is being studied in a number of other ongoing clinical trials, in a number of different indications, and has to date shown a manageable safety and tolerability profile.

The types of risks with the combination of durvalumab + tremelimumab (based on an equivalent durvalumab dose of 20mg/kg and a tremelimumab dose of 1mg/kg) are similar to those for durvalumab and tremelimumab monotherapy. Emerging data from study 006, other studies evaluating the combination, and from combinations of other agents in the same class indicate an increased frequency and/or severity of some of these immune-mediated toxicities.

For information on all identified and potential risks with the durvalumab+tremelimumab combination please always refer to the current version of the durvalumab IB

In durvalumab+tremelimumab combination studies at the dose of durvalumab 20mg/kg and tremelimumab 1mg/kg AEs (all grades) reported very commonly ($\geq 10\%$ of patients) are fatigue, diarrhoea, nausea, dyspnea, decreased appetite, pruritus, vomiting, anaemia, constipation, cough, abdominal pain, pyrexia, back pain, arthralgia, hypothyroidism, asthenia, oedema peripheral, weight, decreased hyponatraemia and rash.

Approximately 15% of patients experienced an AE that resulted in permanent discontinuation of study drug and approximately 15% of patients experienced an SAE that was considered to be related to durvalumab and tremelimumab by the study investigator.

A detailed summary of durvalumab + tremelimumab combination AE data can be found in the current version of the durvalumab IB.

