13. STATISTICAL CONSIDERATIONS

13.1 Study Design/Endpoints

13.1.1 Primary Endpoint: The primary endpoint of this study is overall response rate as determined by RECIST 1.1.

13.1.2 Secondary Endpoints: Secondary endpoints include progression-free and overall survival, overall response according to irRC, and assessments of safety.

Clinical laboratory tests, vital signs and weight measurements, physical exams, performance status evaluations, imaging scans and any other medically indicated assessments, including subject interviews, will be performed to detect new abnormalities and deteriorations of any pre-existing conditions.

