13.3 Randomization

13.3.1 NSCLC

Patients enrolled in the NSCLC cohort will be randomly assigned in equal proportions to therapy with MEDI4736(durvalumab)/tremelimumab alone, MEDI4736(durvalumab)/tremelimumab with low-dose RT, or MEDI4736(durvalumab)/tremelimumab with high-dose RT. Forty patients will be assigned to each of the three therapies (120 in total).

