13.8 Analysis of Secondary Endpoints

13.8.1 Safety

Assessments of safety and tolerability will be performed on an ongoing basis. At the conclusion of the study, safety data will be summarized for each treatment arm within each cohort. The proportions of subjects with grade-3 or higher adverse events will be presented with exact binomial confidence intervals. Although it is unexpected after a successful early safety assessment, if at any time after the early safety review 33% or more of patients in a cohort are observed with severe toxicities, the regimen in that cohort will pause and a comprehensive safety analysis will be conducted.

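### NSCLC interim safety rule attributes toxicity to radiation from RT-arm data alone, and no safety contrast with the randomised drug-only arm is planned

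*Combined protocol and SAP*

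**What the plan says.** The first NSCLC primary objective (section 1.1) is "To assess safety and tolerability of combined checkpoint blockade with MEDI4736(durvalumab) and tremelimumab alone or with high or low-dose radiation in NSCLC". Section 13.3.1 randomises 120 patients equally to three arms of 40, and one of these (Arm C) receives the two drugs without radiation.

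The early look in section 13.6 is a "complete review of the adverse event data for the first 10 patients assigned to MEDI4736(durvalumab)/tremelimumab/high-dose RT" and for the first 10 on low-dose RT. Arm C is not named. If at least three patients in an RT arm have a DLT, "the addition of RT will be considered too toxic and enrollment to that arm will stop". Section 5.2 carries the same rule.

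The DLT definition in section 5.2 lists events that the drugs produce on their own, including grade 4 immune-related events, grade 3 or higher colitis, pneumonitis and marked transaminase elevation. It excludes toxicity clearly due to the cancer or to some other cause, but does not name study-drug toxicity as an exclusion.

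For the final analysis, section 13.8.1 summarises safety by arm: "The proportions of subjects with grade-3 or higher adverse events will be presented with exact binomial confidence intervals". It plans no difference, interval for a difference, or test against Arm C. Sections 13.7, 13.8.2 and 13.8.3 plan RT-versus-control comparisons for response, PFS, OS and irRC response.

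**The concern.** Saying that adding RT is too toxic is a statement about a difference: toxicity with RT compared with toxicity without it. The rule reaches it from the RT arm's count alone, although patients randomised to the same drugs without RT are available. An arm could therefore be closed with radiation named as the cause when the drugs explain the events.

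A triggered stop would end one of the two pairwise response comparisons that section 13.4.1 is built on. Under the same section Arm C keeps enrolling while the other RT arm is open. The final safety analysis supplies no planned estimate that could correct the attribution.

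The colorectal rule in section 13.6 shows that the attribution is not needed. In a cohort with no drug-only arm, it stops enrolment to the arm and names no cause.

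**Working it through.** **1. Reproduce the plan's table (section 13.6).** With 10 patients and true rate p,

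P(X ≥ 3) = 1 − Σ C(10, x) p^x (1 − p)^(10 − x), for x = 0, 1, 2.

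At p = 0.15 this is 1 − (0.1969 + 0.3474 + 0.2759) = 0.180.

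| True rate | Printed | Exact |
|---|---|---|
| 10% | 0.07 | 0.0702 |
| 15% | 0.18 | 0.1798 |
| 20% | 0.33 | 0.3222 |
| 25% | 0.47 | 0.4744 |
| 30% | 0.62 | 0.6172 |

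The table is reproduced, apart from a rounding slip in the 20% row. It is labelled for severe or unexpected toxicity, whereas the NSCLC rule counts DLTs.

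**2. Read p as the drug-only DLT rate, with no toxicity added by RT.** Each probability is then the chance that an RT arm is labelled too toxic although RT contributed nothing. The two arms contain different patients, so the chance that at least one is so labelled is 1 − (1 − P)².

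| Assumed drug-only DLT rate | One RT arm | At least one of two |
|---|---|---|
| 10% | 0.070 | 1 − 0.9298² = 0.135 |
| 15% | 0.180 | 1 − 0.8202² = 0.327 |
| 20% | 0.322 | 1 − 0.6778² = 0.541 |

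**3. Status of the assumed rate.** The nearest figure in the documents is in section 2.2.2.1: "approximately 15% of patients experienced an SAE that was considered to be related to durvalumab and tremelimumab" (section 2.2.1 gives about 13%). These are related-SAE rates from other combination studies and are not tied to the first 4 weeks, which is the DLT period in section 5.2. They are not DLT rates, so the 10% to 20% range is an assumption.

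**4. What a final contrast would deliver.** For a difference in proportions with 40 per arm and a common rate p, the 90% half-width is 1.645 × √(2p(1 − p)/40):

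- p = 0.15: 1.645 × √0.006375 = 0.131
- p = 0.30: 1.645 × √0.0105 = 0.169
- p = 0.40: 1.645 × √0.012 = 0.180

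As a one-sided 0.10 test, 80% power needs roughly 15% vs 35%, or 30% vs 53%.

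**5. What 10 vs 10 would deliver at the interim.** At p = 0.15 the half-width is 1.645 × √(2 × 0.1275/10) = 0.26. The Arm C count can give context at that point but cannot settle attribution.

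**The case against.** The strongest defence is that stopping on an RT arm's own count protects patients whichever component is responsible. That stands: the fault lies in the conclusion attached to the stop, not in the stop.

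The objective says to assess safety, while the next objective, on response, says to compare. Section 13.1.2 adds that "Secondary endpoints include progression-free and overall survival, overall response according to irRC, and assessments of safety". A reader might infer that omitting a safety comparison contradicts a primary objective. It does not, because per-arm rates with intervals can answer an objective to assess.

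A reader might also infer that drug toxicity will be taken for radiation toxicity at the end of the trial. Section 13.8.1 reports Arm C beside the RT arms, so an informal comparison remains possible; the supportable word is can.

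A third tempting step is to treat 15% as the background DLT rate and quote 0.33 as the trial's false-label risk. As working step 3 shows, the event and the window both differ. Section 3.2.25.1 also excludes NSCLC patients with grade 3 or higher immune-related events on prior immunotherapy.

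Some safeguards exist. Section 4.3.2 mentions an early safety look after 10 patients per arm. Section 5.2 provides for review of the high-dose arm's data and a possible amendment if that arm triggers. Section 12.1 gives the principal investigator and statistician continuous data access. None of these sets an RT arm against Arm C.

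**Conclusion.** The point holds in limited form. The NSCLC interim rule states a comparative conclusion that its single-arm data cannot support, and no planned analysis estimates the toxicity added by RT, although the randomised control is there to do so.

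With no added RT toxicity, the wrong label falls on a given RT arm with probability 0.07 to 0.32, and on at least one arm with probability 0.135 to 0.54, over assumed drug-only DLT rates of 10% to 20%. The documents do not locate the true rate within or outside that range. They do not support reading this as a broken primary objective, an unjustified stop, or a certain misattribution.

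**What to change.** **Sections 5.2 and 13.6.** Leave the enrolment rule unchanged. Remove the statement that adding RT is too toxic and say only that enrolment to that arm stops, as the colorectal rule does. Tabulate the DLT count for the first 10 Arm C patients at the same review, as descriptive context. The sponsor must first reconcile the timing of that review, which comes after one cycle in section 13.6 and after two cycles in section 5.2.

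**Section 13.8.1, cohort 1.** Add the difference in the proportion with grade 3 or higher adverse events, each RT arm minus Arm C, with a 90% confidence interval (the level section 13.7 uses for response). Base any statement about toxicity added by RT on that difference.

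**Cost.** One extra column at the review, one reworded sentence and one extra table, all from data already collected. The interval is wide: at a 30% rate in both arms and an observed difference of zero, it would still reach an excess of about 17 percentage points. If an RT arm has closed after 10 patients, it is wider still: 1.645 × √(0.21/10 + 0.21/40) = 0.27 against 40 in Arm C. The report should therefore present an estimate and its limits, not a claim that RT adds no toxicity.
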